APPENDIX A. GUIDANCE ON SAFETY MONITORING

1. Guidance on Monitoring Subjects with Elevated Liver Function Tests

Liver enzymes (ALT, AST, GGT, ALP), as well as total bilirubin⁴ will be measured at each study visit.

In any case of elevated ALT or AST to a level exceeding of $\geq 2x$ ULN (including subjects whose baseline ALT or AST levels are $\geq 2x$ and $\leq 3x$ the ULN, who may be enrolled in the study), a thorough medical history and physical examination with a focus on liver disease should be undertaken⁵. In addition, the subject should be instructed to refrain from alcoholic beverages.

In case of symptoms compatible with drug-induced liver injury, the subject should be invited for an unscheduled visit to measure liver enzymes as soon as possible.

Solitary elevations of total bilirubin, not accompanied by elevations of ALT or AST should be managed according to the discretion of the Treating Physician.

1.1. Elevation of Either ALT or AST to ≥ 3 x ULN:

Confirmation of the abnormality (in case the abnormality is of ALT or AST ≥ 8 times the ULN, no confirmation is required prior to study drug discontinuation, but the assessments below should be performed):

- The day in which the abnormal value is received from the laboratory will be considered as Day 0.
- The Investigator should repeat the test before Day 2, for confirmation purposes (this may be performed in a local laboratory along with CBC and differential to assess for eosinophilia. In general, in case a blood sample is sent to a local laboratory, the following assessments [and reference ranges] are mandatory: ALT [serum glutamic pyruvic transaminase; SGPT], AST [serum glutamic oxaloacetic transaminase; SGOT], ALP, total bilirubin, CBC [with differential for eosinophil count, separate tube], and INR [separate tube; not to be sent in a confirmatory test]). The investigator should also question the subject regarding symptoms.

The abnormality will be regarded as confirmed in each of the following scenarios:

1. In case baseline value was within normal range and ALT or AST is still $\geq 3x$ ULN
2. In case baseline value was above ULN and ALT or AST is ≥ 2 times the baseline value.

Upon confirmation of the abnormality as noted above, the following additional evaluations should be performed and results should be recorded in the eCRF.

⁴ In case total bilirubin is $>ULN$, then direct bilirubin will be checked.

⁵ Thorough medical history with a focus on liver disease: Personal or family history of liver disease; personal history of a systemic disease with potential liver involvement; exposure to alcohol, medications (prescription or OTC), herbal preparations, dietary supplements, recreational drugs, special diets or environmental chemical agents; potential exposure to infectious agents (eg, travel to developing countries, history of potential exposure to blood or blood products, high-risk sexual relations) and any additional information deemed relevant by the investigator. Physical examination – including signs of chronic liver disease.

Additional Tests/Evaluations

- Serology for Hepatitis A (antibody, immunoglobulin M and G), B (core antibody total, core immunoglobulin M, and surface antigen), and C viruses (central laboratory).
- Serology for autoimmune hepatitis: anti-nuclear antibodies (titer), ASMA (Anti Smooth Muscle Antibodies), anti-LKM (Liver Kidney Microsomal) antibodies (central laboratory). Further testing may be required in case of a positive result for Hepatitis B or C.
- An ultrasound examination of the liver and biliary tract.
- Other diagnostic tests/consultations, as deemed necessary by the investigator e.g. serology for hepatitis E virus in case of travel to endemic geography)

Observation and Follow-Up (to be performed after the abnormality was confirmed as above)

1.1.1. ALT or AST $\geq 3x$ ($>3.5x$ ULN if baseline value is $>2.5x$ ULN) but less than $5x$ ULN

In addition to the above procedures required for any elevation to levels $>3x$ ULN:

- ALT, AST, GGT, ALP, total and direct bilirubin, CBC and differential (to assess for eosinophilia) and INR should be monitored on days 5 (± 2), 8 (± 2), 14 (± 3), and 28 (± 3). On at least 1 of these days, the test should be performed centrally. (INR should be sent to a local laboratory only.)
- In cases where a local laboratory is used, the results should be recorded in the eCRF, accompanied by the reference range of the relevant measurements.
- Should the abnormality ($\geq 3x$ ULN in case baseline within normal range or $\geq 2x$ ULN in case the baseline value was above ULN, but still $<5x$ ULN) persist further, the subject will be followed according to the investigator's discretion, but at least once a month a blood sample for ALT, AST, GGT, ALP, and total and direct bilirubin should be sent to the central laboratory.

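### Appendix A schedules no INR for a repeat ALT/AST between 3×ULN and twice baseline when baseline exceeds 1.5×ULN, although the INR stopping rule applies from 3×ULN

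*Protocol*

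**What the plan says.** Appendix A, item 1, of the protocol builds liver monitoring in steps.

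- **Trigger (1.1).** ALT or AST of at least 3×ULN calls for a repeat before Day 2.
- **Confirmation (1.1).** With a normal baseline, the repeat confirms if it is still at least 3×ULN. With a raised baseline, the scenario is "In case baseline value was above ULN and ALT or AST is ≥ 2 times the baseline value".
- **Content of the repeat (1.1).** The general rule is that "in case a blood sample is sent to a local laboratory, the following assessments [and reference ranges] are mandatory". The list includes total bilirubin, and it names INR with an exception: "INR [separate tube; not to be sent in a confirmatory test".
- **Follow-up.** The heading is "Observation and Follow-Up (to be performed after the abnormality was confirmed as above". Under it, 1.1.1 (3 to below 5×ULN) sets INR on days 5, 8, 14 and 28, and 1.1.2 (5 to below 8×ULN) sets INR twice a week.
- **Stopping (1.2).** Drug stops at once if ALT or AST is at least 3×ULN with INR above 1.5 or total bilirubin above 2×ULN. Section 7.1.1 requires cessation and SAE reporting on essentially the same combination. Neither depends on baseline or on confirmation.
- **Eligibility.** Exclusion f (Section 4.2) bars ALT or AST of 2×ULN or more at screening. Appendix A still describes patients with baselines of 2 to 3×ULN as ones "who may be enrolled in the study".

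**The concern.** The stopping rule needs two measurements, an enzyme value and an INR or bilirubin. For a patient with a raised baseline, the enzyme half can be met by a repeat that the plan does not count as confirmed. In that situation the plan leaves INR out of the repeat and does not start the INR schedule. INR is also absent from the chemistry, hematology and urgent safety panels (Sections 7.3.1, 7.3.2 and 7.3.4), so no other scheduled test supplies it.

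A patient with a normal baseline and the same repeat value would have INR measured four times in 28 days. The patient who started with worse liver tests gets none on schedule. At stake is a stopping criterion that cannot be assessed as written in a narrow group.

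**Working it through.** The protocol gives no figure to reproduce; the check is a comparison of thresholds. Write baseline as b×ULN with b above 1.

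**Step 1: where the gap opens.** Confirmation needs a repeat of at least 2b. The stopping rule starts at 3. A gap exists when 2b > 3, that is, b > 3/2 = 1.5. It covers repeats from 3 up to, but not including, 2b.

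| Baseline b (×ULN) | Confirms at 2b | Repeats of 3×ULN or more left unconfirmed |
|---|---|---|
| 1.5 | 3.0 | none |
| 1.6 | 3.2 | 3.0 to <3.2 |
| 1.75 | 3.5 | 3.0 to <3.5 |
| 1.99 | 3.98 | 3.0 to <3.98 |
| 2.0 | 4.0 | 3.0 to <4.0 |
| 2.5 | 5.0 | 3.0 to <5.0 |
| 3.0 | 6.0 | 3.0 to <6.0 |

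**Step 2: who can be in it.** Exclusion f leaves screening values just under 2×ULN, which gives the rows down to 1.99. It applies at screening, so a baseline-visit value could be somewhat higher. Section 16.1 records that Amendment 04 made this criterion more stringent, and Section 3.1 says that 123 patients had been randomized before 10 January 2016. Of those, 30 were in the 1.5 mg arm and had drug stopped, leaving 123 − 30 = 93 in the continuing arms. The protocol does not say how many of these, if any, had baselines of 2 to 3×ULN.

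**Step 3: is it a consistent baseline-relative design?** Two parts of 1.1.1 say otherwise.

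- Its heading raises the entry level to more than 3.5× "ULN if baseline value is" above 2.5×ULN, and the range ends below 5×ULN. For b > 2.5, 2b exceeds 5, so no confirming repeat can fall in that range.
- Its persistence bullet sets the abnormality at 2× "ULN in case the baseline value was above ULN, but still" under 5×ULN. That is twice ULN, not twice baseline as in 1.1.

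For b above 2.5 the gap also covers 5 to below 2b, where the twice-weekly INR of 1.1.2 is not triggered either.

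**Step 4: size.** The protocol gives no distribution of baselines, so these inputs are assumptions, apart from two:

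- 200 active patients (100 in each of two active arms, Section 3.1);
- 1% to 5% of them with baseline 1.5 to 2×ULN (assumed);
- 3.4% to 20% of those reaching 3 to 5×ULN. The lower figure is the rate of ALT above 3 and up to 5×ULN on 0.6 mg from a normal baseline (Table 2); the upper is assumed;
- half of those falling in the gap (assumed).

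Low: 200 × 0.01 × 0.034 × 0.5 = 0.034. High: 200 × 0.05 × 0.20 × 0.5 = 1.0. So about 0.03 to 1 patient in the whole trial.

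**The case against.** The other side has several fair arguments.

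- **Few patients, little harm.** The estimate is one patient or fewer. A missed stop further requires an INR above 1.5 with bilirubin not above 2×ULN, no listed symptoms and no eosinophilia. Section 1.4.1.2 reports that Hy's law criteria were not met in the MS experience at 0.6 mg/day. This stands, although the present trial goes to 1.0 mg.
- **Other safeguards.** Total bilirubin is measured at each study visit and is mandatory in a local-laboratory repeat. The rules for symptoms, eosinophilia, persistent values of 5×ULN or more, values of 8×ULN or more, and liver impairment (Section 3.6) all remain. Exclusions i.7 and j will remove some patients with raised baselines. An investigator may order INR at any time. With suggestive symptoms "the subject should be invited for an unscheduled visit to measure liver enzymes as soon as possible", and a non-confirmatory sample sent to a local laboratory must include INR. All of this stands. It narrows the gap to the INR half of one rule but does not close it.
- **Requiring a doubling is a legitimate choice.** Asking more of a raised baseline before starting a full work-up is defensible. Lowering that threshold to 3×ULN would trigger the work-up after a 3.0/2.5 = 1.2-fold rise at a baseline of 2.5×ULN. This is a good reason to leave the confirmation threshold alone. It does not justify withholding INR when the stopping rule ignores baseline.

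**Conclusion.** The inconsistency is real and minor. For baselines above 1.5×ULN, a repeat from 3×ULN to just under twice baseline meets the enzyme half of a mandatory stopping rule while no INR is scheduled. The threshold result follows from the text alone. The estimate of about one patient or fewer rests on the assumed inputs above.

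A reader might infer more, in three ways that the protocol does not support.

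- *That such a patient is denied serology and ultrasound.* The wording is ambiguous. Section 1.1 ties these to confirmation, but 1.1.1 to 1.1.3 each refer back to procedures required for any elevation above 3×ULN.
- *That the whole stopping rule fails.* Only its INR half lacks a scheduled measurement; the bilirubin half can be assessed.
- *That the wide gap up to just under 6×ULN is open to new patients.* Current exclusion f bars screening values of 2×ULN or more. The wide interval concerns earlier-enrolled patients with such baselines, and no count of them is given.

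**What to change.** In Appendix A 1.1, delete the exception that keeps INR out of the confirmatory test. Require a local-laboratory INR with every repeat ALT/AST prompted by a value of at least 3×ULN, whatever the baseline and whether or not the repeat confirms. This closes the gap for all baselines, including 3.0 to 3.5×ULN when baseline is above 2.5×ULN. The cost is one extra tube per repeat.

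Two corrections belong in the same edit: remove the outdated statement that patients with baselines of 2 to 3×ULN may be enrolled, and reconcile the 3.5×ULN clause of 1.1.1 with the confirmation rule, since no confirming repeat can reach it.

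Changing the twice-baseline threshold for the full work-up is optional. It trades specificity for sensitivity and is not needed to resolve this point.

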- all events of possible drug-induced liver injury with hyperbilirubinemia (defined as AST or ALT ≥ 3 times the ULN, plus either bilirubin ≥ 2 times the ULN or International Normalized Ratio [INR] > 1.5) or Hy's Law events require immediate study treatment cessation and reporting as a serious adverse event.

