7.3.1. Serum Chemistry

The following serum chemistry tests will be performed at all scheduled visits:

- calcium
- phosphorus
- sodium
- potassium
- chloride
- bicarbonate and carbon dioxide
- glucose
- blood urea nitrogen (BUN)
- creatinine (Note: Estimated creatinine clearance will be calculated at all in-clinic study visits.)
- uric acid
- ALT
- AST
- lactic dehydrogenase (LDH)
- gamma-glutamyl transpeptidase (GGT)
- alkaline phosphatase

- creatine phosphokinase (CPK)
 - In case of CPK results >ULN, troponin and creatine kinase MB isoenzyme (CK-MB) will be tested by the central laboratory.
 - In case of CPK>10×ULN, an unscheduled visit to assess urine myoglobin will be required. The following blood tests will be repeated at the unscheduled visit: CPK, blood urea nitrogen, creatinine, electrolytes including potassium, calcium, phosphate.
- total protein
- albumin
- Fibrinogen
- CRP
- pancreatic amylase
 - Lipase will be tested in case of abnormal pancreatic amylase results
- total bilirubin
 - Only if total bilirubin is elevated, the following tests will be performed:
 - direct bilirubin
 - indirect bilirubin
- lipid profile [total cholesterol, high density lipoprotein (HDL), low density lipoprotein (LDL), triglycerides] - **at baseline and Month 12 only**
- thyroid function (T3, T4, TSH) – **at baseline, Months 6 and 12 only**

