1.1.3. ALT or AST $\geq 8x$ ULN

In addition to the above procedures required for any elevation to levels $>3x$ ULN:

- The study drug should be discontinued immediately and the ETD visit should be performed.
- For follow-up guidance, please see below section "Follow-Up of Liver Enzymes After Stopping-Rules Are Met".

1.2. Stopping Rules:

In the following circumstances, the study drug will be discontinued immediately:

- Any increase in ALT or AST to $\geq 3xULN$, combined with INR >1.5 or total bilirubin $>2xULN$
- Any increase in ALT or AST to $\geq 3xULN$, which is accompanied by nausea, vomiting, fever, rash, or eosinophilia
- Any increase in ALT or AST to levels $\geq 5x$ but $<8xULN$, which is persistent for ≥ 2 weeks of repeated measurements
- Any increase in ALT or AST to levels $\geq 8xULN$
- In any case where monitoring of liver enzymes cannot be performed according to the protocol guidance

1.2.1. Follow-Up of Liver Enzymes After Stopping-Rules Are Met:

- A subject who meets the above criteria for discontinuation of the study drug should be invited to the site to return the study drug. ETD visit activities should be performed as soon as possible.
- Liver enzymes should be monitored until normalization or stabilization of the abnormality, according to the discretion of the investigator.
- In any case, following ETD, the minimal follow-up period will be 30 days and will include measurement of liver enzymes at least once weekly (may be performed in a local laboratory, with at least 1 test being sent to the central laboratory).
- Every effort should be made to complete the additional tests/ evaluations, as described above.

2. Use of Moderate/Strong CYP3A4 Inhibitors

Laquinimod PK is affected by moderate and strong CYP3A4 inhibitors; therefore, moderate/strong CYP3A4 inhibitors are disallowed during study and 30 days after the last dose has been administered. A partial list of commonly used CYP3A4 inhibitors is presented in [Appendix B](#).

3. Use of CYP3A4 Substrates with Narrow Therapeutic Index

Plasma levels of drugs that are CYP3A4 substrates may increase when combined with laquinimod. Patients taking drugs that are metabolized by CYP3A4, specifically those with a Narrow Therapeutic Index ([Table 6 in Appendix C](#)) should be advised that plasma levels of these drugs could increase when combined with laquinimod.

4. Use of CYP1A2 Substrates

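### Appendix A confirms a liver-enzyme rise from a raised baseline only at twice baseline, which conflicts with its own 3×ULN follow-up tier and, for baselines above 1.5×ULN, leaves a narrow band with no scheduled INR

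*Protocol*

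**What the plan says.** **Stopping rule.** Appendix A, 1.2 discontinues drug immediately when ALT or AST reaches 3×ULN "combined with INR >1.5 or total bilirubin" above 2×ULN. Section 7.1.1 states a matching rule (with bilirubin at or above 2×ULN): such "events require immediate study treatment cessation and reporting as a serious adverse event". Neither adjusts for baseline.

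**Confirmation.** Appendix A, 1.1 asks for a repeat before Day 2. If baseline was normal, the rise is confirmed when the repeat is still at least 3×ULN. Otherwise scenario 2 applies: "In case baseline value was above ULN and ALT or AST is ≥ 2 times the baseline value".

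**Where INR is measured.** The list in 7.3.1 opens "The following serum chemistry tests will be performed at all scheduled visits" and does not contain INR. Neither do the hematology list (7.3.2) or the urgent panel (7.3.4). Appendix A, 1.1 makes INR mandatory in local-laboratory samples, with one exception: "separate tube; not to be sent in a confirmatory test". Scheduled INR appears in 1.1.1 (Days 5, 8, 14 and 28) and 1.1.2 (twice weekly), both under a heading that says these steps are "to be performed after the abnormality was confirmed as above".

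**Thresholds in 1.1.1.** Its heading covers ALT or AST from 3×ULN (above 3.5×ULN if baseline exceeds 2.5×ULN) to below 5×ULN. Its third bullet sets the level for continued follow-up at 2× "ULN in case the baseline value was above ULN, but still" below 5×ULN.

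**Who can enter.** Exclusion f removes patients with ALT or AST of 2×ULN or more at screening, so values between 1.5 and 2×ULN are admissible.

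**The concern.** A stopping rule needs its input to be measured when its threshold is crossed. Here the enzyme threshold is fixed at 3×ULN, while the step that opens scheduled INR is relative to baseline. Once the baseline is high enough, the second threshold passes the first. Scenario 2 also disagrees with the heading of the follow-up tier to which it leads.

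At stake is one limb of the liver stop and of the matching SAE trigger, in patients who entered with raised enzymes. The affected range lies where laquinimod shows its ALT signal: in Table 2, 30 of 888 patients on 0.6 mg had a highest ALT above 3 and up to 5×ULN, against 5 of 930 on placebo. Above 5×ULN the counts are 10 and 13.

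**Working it through.** The protocol gives no figure of its own here, so there is none to reproduce.

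**1. Where the thresholds cross.** Write B for baseline in multiples of ULN, with B above 1. Scenario 2 confirms at 2B; the stop acts at 3. The uncovered band runs from 3 to just under 2B and exists when 2B > 3, that is, B > 1.5.

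| Baseline B (×ULN) | Confirmed at 2B | Band without scheduled INR |
|---|---|---|
| 1.2 | 2.4 | none |
| 1.5 | 3.0 | none |
| 1.6 | 3.2 | 3.0 to <3.2 |
| 1.75 | 3.5 | 3.0 to <3.5 |
| 1.9 | 3.8 | 3.0 to <3.8 |
| 1.99 | 3.98 | 3.0 to <3.98 |

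Example: B = 1.9 and a repeat of 3.5 give 3.5/1.9 = 1.84, below 2, so the rise is unconfirmed.

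**2. Scenario 2 against the 1.1.1 heading.** The heading provides for baselines above 2.5×ULN with values above 3.5 and below 5×ULN. Under scenario 2 such a patient is confirmed only above 2 × 2.5 = 5×ULN. The parenthesis in the heading can therefore never apply, so the two provisions cannot both be right.

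**3. How many patients.** From sections 1.4.1.2 and 9.2 and Table 2: 983 patients on 0.6 mg, 888 with normal baseline ALT, 30 of those 888 with a highest ALT above 3 and up to 5×ULN, and 200 active patients planned here. The ten patients above 5×ULN are left out because the band ends below 4×ULN.

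- Raised or missing baseline ALT: (983 − 888)/983 = 9.7%; × 200 = 19.3 patients.
- Assumed share with baseline above 1.5×ULN, 10% to 40%: 1.9 to 7.7 patients.
- Rate of 30/888 = 3.4%, multiplied by an assumed 1 to 5 for raised baselines.
- Low: 1.93 × 0.0338 × 1 = 0.07. High: 7.73 × 0.0338 × 5 = 1.3.

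For AST the same steps with 950 and 9/950 give (983 − 950)/983 × 200 = 6.7; × 10% to 40% = 0.67 to 2.7; × 0.0095 × 1 to 5 = about 0.01 to 0.13.

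**4. Effect of a whichever-is-lower rule.** Confirmation stays at 2.4 for B = 1.2 and at 3.0 for B = 1.5, and falls to 3.0 for B = 1.6, 1.75, 1.9 and 1.99. The band is then empty for every baseline that exclusion f admits. A flat 3×ULN would be worse: a baseline of 1.2 with a repeat of 2.8 (2.33 times baseline) is confirmed now and would be lost.

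**The case against.** The best reply is that the 1.1.1 heading already starts its tier at 3×ULN for every baseline up to 2.5×ULN, and that its third bullet follows raised baselines from 2×ULN. On that reading INR is scheduled across the whole band. It is a fair account of what was probably intended. But it works only by overriding the stated condition that follow-up comes after confirmation, so it establishes the conflict with scenario 2 and does not remove it.

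Second, doubling a raised baseline is a legitimate baseline-relative criterion, and INR is left out of the confirmatory test for everyone. That omission looks deliberate, and I do not treat it as an error.

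Third, a reader might infer that INR cannot be obtained in the band, or that these patients go unmonitored. The protocol does not support that. Section 3.11.5 allows other procedures at the investigator's discretion, and any non-confirmatory local-laboratory sample must include INR, for example at the unscheduled visit that Appendix A requires for compatible symptoms. The repeat test, symptom questioning, liver-focused history and examination, and the bilirubin, symptom and eosinophilia limbs all still apply. Nor can one conclude that serology and ultrasound are missing: 1.1.1 opens "In addition to the above procedures required for any elevation to levels" above 3×ULN and can be read as requiring them.

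**Conclusion.** The point holds as a drafting conflict with a small safety consequence. Read literally, a patient with a baseline above 1.5 and below 2×ULN, and a repeat from 3×ULN to just under twice baseline, falls outside the scheduled Day 5, 8, 14 and 28 follow-up and its INR, although INR above 1.5 would require a stop and an SAE report.

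About 0.07 to 1.3 active patients would be in the band for ALT, with at most about 0.1 more for AST. The 10% to 40% share and the 1-to-5 multiplier are my assumptions. Table 2 describes 0.6 mg for up to 2 years, against 12 months at 0.5 and 1.0 mg here. The baseline count mixes raised with missing values. On those assumptions the range leans high, because the 3-to-5×ULN tier is wider than the band and the repeat must also stay below twice baseline.

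These are patients with raised enzymes. It would be wrong to read them as missed stops, which would also need INR above 1.5 while no other limb is met. The protocol gives no rate for that, and section 1.4.1.2 reports no case meeting Hy's law criteria in the pivotal MS studies. Month 12 UHDRS-TMS is not affected. Severity: minor safety correction.

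**What to change.** Reword scenario 2 in Appendix A, 1.1: with a baseline above ULN, the rise is confirmed if the repeat ALT or AST is at least 2 times baseline or at least 3×ULN (above 3.5×ULN if baseline exceeds 2.5×ULN), whichever is lower. This brings the affected patients into the existing INR schedule, agrees with the 1.1.1 heading and keeps the more sensitive trigger for baselines of 1.0 to 1.5×ULN. The cost is one sentence and the full liver work-up for up to about one or two more patients.

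Sending INR with the confirmatory repeat is optional. It would also cover values between 3.0 and 3.5×ULN at baselines above 2.5×ULN, which the reworded rule still leaves out. Appendix A, section 1 still describes enrolled baselines of 2 to 3×ULN, although exclusion f now bars them at screening. The price is local-laboratory handling for repeats that might otherwise go to the central laboratory.

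Separately, the bilirubin cut-off is above 2×ULN in 1.2 and at or above 2×ULN in 7.1.1; the two should be aligned.
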